5.6. Premature Termination of Trial/Closure of Center

The sponsor may discontinue the trial at any time. Reasons for discontinuation of the trial may include, but are not limited to, new information on safety or efficacy, requests from regulatory authorities, changes in business priorities, or study termination upon review of the recommendations/findings of the DMB. Additional reasons for center closure may include, but are not limited to, excessive protocol violations, inadequate regard for subject safety, failure to follow recommended procedures (e.g., documentation), failure or inability to accommodate Avid/Contract Research Organization (CRO) monitors or to provide required access to data and source documents, staff turnover or inadequate staffing, and inadequate enrollment. Except in cases affecting subject safety, the investigators will be given a minimum of 30 days to complete final study evaluations for ongoing subjects. In all cases of center or study termination, appropriate steps will be taken to ensure the safety of study subjects.

6. **PRODUCT RISK ASSESSMENT**

The most up-to-date and complete information regarding the use of ¹⁸F-AV-1451 Injection can be found in the investigator's brochure.

In brief, ¹⁸F-AV-1451 Injection is an experimental imaging agent that will be used at relatively low (tracer) doses. Because ¹⁸F-AV-1451 Injection is under clinical investigation, it is recommended that subjects receiving ¹⁸F-AV-1451 Injection be followed closely by means of adverse event reporting and vital signs.

There are no data on the effects of ¹⁸F-AV-1451 Injection in human perinatal development. For this reason, females must avoid becoming pregnant. Both females and males must use adequate contraceptive methods for 24 hours after administration of ¹⁸F-AV-1451 Injection. ¹⁸F-AV-1451 Injection must not be administered to females who are pregnant or lactating. Males with female partners who are pregnant or of childbearing potential must agree to refrain from sexual activity for 24 hours following administration of ¹⁸F-AV-1451 Injection. Additionally, males must agree not to donate sperm for 24 hours following administration of ¹⁸F-AV-1451 Injection.

7. **PROCEDURES AND METHODS**

7.1. Assessment Periods

See Section 11.2, Trial Flow Chart

7.1.1. Screening Visit:

Screening may take place over several days and can occur at multiple locations (e.g. hospice, subject's home, research office, or clinic). All screening assessments will preferably be performed within 45 days prior to the PET imaging session. Some screening assessments may be performed on the imaging day prior to injection with sponsor approval. Screening assessments will include:

- 1. Informed consent (for clinical, imaging and autopsy procedures);
- 2. Obtain historical brain MRI images if available;
- 3. Demographics and baseline characteristics (e.g. birth year, gender, race, ethnicity, education);
- 4. Medical history and concomitant medications;
- 5. Brief physical and neurological exam;
- 6. Neurologic disease history (if relevant: date or months since symptom onset, date or months since diagnosis, family history of neurologic disease);
- 7. Mini-Mental Status Examination (MMSE) may be obtained if the subject is able to cooperate with the test;
- 8. Caregiver or informant to complete IQCODE;
- 9. Urine pregnancy test (for females of childbearing potential);
- 10. Vital signs, including the most recent height and weight which will be collected from subject's previous medical record; and
- 11. A physician or appropriate designee evaluation and summary of current medical status.

7.1.2. ¹⁸F-AV-1451 PET Imaging Visit(s):

- 1. The subject will be seen by a physician prior to dose administration who will assess their ability to safely tolerate the imaging procedure;
- Females of childbearing potential will have a urine (or serum if required by local IRB) pregnancy test prior to injection (the result must be negative for the subject to be administered ¹⁸F-AV-1451);
- 3. A target dose of 370 MBq (10 mCi) of ¹⁸F-AV-1451 will be administered intravenously and a 20-minute continuous brain PET imaging will begin 80 minutes post injection;
- 4. Images will be reconstructed and reviewed immediately after completion of the scan;
- 5. Vital signs will be taken immediately prior to administration of ¹⁸F-AV-1451, and after completion of imaging, prior to discharge;
- 6. Subjects will be observed continuously for signs of adverse events (AE) or serious adverse events (SAE). All AEs and SAEs will be followed until resolution;

- 7. The injection site will be observed for excessive inflammation or damage to the surrounding tissue where the dose was injected; and
- 8. A physician will see the subject prior to discharge to evaluate the subject's readiness for discharge.

Follow-Up Phone Call:

A follow-up phone call to the subject, (or caregiver/informant if applicable), will be conducted within 2 or 3 business days of the imaging day, but not before 48 hours post-injection, to confirm subject well-being and to collect information about any new adverse events. If both of these days are not business days, the follow-up phone call can occur the following business day. End of study for the purpose of adverse event reporting is defined as the completion of the follow-up phone call.

7.1.3. Death and Autopsy:

- 1. The responsible family member or caregiver/informant will be contacted immediately after the time of death to obtain a description of events leading up to death;
- 2. Subjects will not have an autopsy performed or be included in the primary analyses if death does not occur within nine months of the most recent imaging session or if tissue has not been acquired before the required number of autopsies for the study has been completed.
- 3. If subject and/or LAR consented, additional research and genetic testing will be performed on brain tissue.

Detailed autopsy procedures are described in the Technical Autopsy Manual.

7.1.4. Additional PET Imaging

If death does not occur within nine months of the ¹⁸F-AV-1451 PET scan, the subject may be given the opportunity to undergo a second ¹⁸F-AV-1451 PET scan and continue in the protocol at the sponsor's discretion. In order to obtain a second scan before the nine month expiry date, it is recommended the second scan be performed any time between six and nine months after the first scan. If the subject agrees to a second ¹⁸F-AV-1451 PET scan, screening assessments will not be repeated. The procedures in Section 7.1.2 will be performed and updated medical history /concurrent medications and an updated neurological disease diagnosis (according to best available information) will be collected. If the subject subsequently comes to autopsy, the second scan (nearest to time of death) will be used in the efficacy analyses. Because cortical tau deposition is expected to occur very slowly, if at all, in cognitively normal (unimpaired) subjects, cognitively normal subjects will not be required to undergo repeat scans. Cognitively normal subjects will remain eligible for autopsy, regardless of time from first scan or second scan to autopsy, and will be included in the primary efficacy cohort if the subject comes to autopsy any time before the trial stopping criteria are met. Subjects of other cognitive status that do not consent to a second ¹⁸F-AV-1451 PET scan will not be included in the primary analyses unless death occurs within nine months of the initial scan.

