AV-1451 was assessed in competitive binding assays against a panel of 72 of the most common central nervous system (CNS) targets and no clinically relevant inhibition was seen. AV-1451 was positive in the in vitro hERG assay; however, in vivo cardiovascular safety pharmacology assessments in dogs showed no evidence of QT prolongation at doses up to 50x the intended maximum human dose (MHD). Nonetheless, until sufficient human cardiovascular safety data are available, clinical studies will exclude subjects with a history of risk factors for Torsades de Pointes and subjects taking drugs known to prolong the QT interval.

In vivo safety pharmacology studies were also conducted in rats to determine potential effects on the CNS and respiratory systems. In these studies no clinically relevant effects were reported at doses exceeding 100x the intended MHD. Additionally, non-radioactive AV-1451 has been tested in single and repeat-dose toxicology studies in rat and dog. In each of these studies the no observable adverse effect levels (NOAELs) were the highest doses tested (150x MHD for single, 50x MHD for repeat).

Potential genotoxicity of non-radioactive AV-1451 was tested in both *in vitro* and *in vivo* assays. In the *in vitro* assays, AV-1451 tested positive for potential genotoxicity. However, in the *in vivo* rat micronucleus assay at doses up to 750x MHD (scaled allometrically), AV-1451 showed no evidence of genotoxicity. The different results in the in vitro genotoxicity assays and the *in vivo* micronucleus study are likely related to differences in the exposure conditions encountered by the target cells in the different test systems. In vivo, AV-1451 is cleared rapidly; however, the *in vitro* experiments employ static, prolonged exposure of cells to high concentrations of the test article. While the *in vitro* data show the potential for genotoxicity, the *in vivo* data provide assurance that genotoxicity is unlikely to occur at clinically-relevant doses for human diagnostic studies.

Three human clinical studies have been completed with ¹⁸F-AV-1451. A total of 59 subjects have been exposed to ¹⁸F-AV-1451 in these studies. The following side effects have been reported in clinical studies: diarrhea, headache, and altered taste. All reported events were mild in intensity and all subjects recovered from these events.

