5. INVESTIGATIONAL PLAN

5.1. Overall Design and Plan of Trial

This study is a clinico-pathological study of the correspondence between ¹⁸F-AV-1451 PET imaging and post-mortem assessment of tau pathology and associated NIA-AA pathological diagnosis.

The screening and imaging procedures have been designed to be tolerable for eligible end-of-life patients. Individuals with terminal medical conditions with projected life expectancy of ≤ 6 months and/or their LAR will provide informed consent. The subject will then receive a PET scan with ¹⁸F-AV-1451 and will be followed to death. Subjects that have a historical brain MRI, acquired within 12 months of the ¹⁸F-AV-1451 PET imaging visit, may consent to have the scan made available to the designated imaging core lab. If death does not occur within nine months of the ¹⁸F-AV-1451 PET scan, the subject may be given the opportunity to undergo a second ¹⁸F-AV-1451 PET scan and continue in the protocol at the sponsor's discretion (screening assessments will not need to be repeated). If the subject subsequently comes to autopsy, the second scan (nearest to time of death) will be used in the efficacy analyses.

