5.2.2. Rationale for Dosage

This trial is designed to evaluate the brain tau protein imaging properties of ¹⁸F-AV-1451 to be used in subjects near end-of-life. ¹⁸F-AV-1451 will be administered IV in a radioactive target dose of 370 MBq with a MHD limited to 20 μ g of compound by mass. This dose is 150-fold lower than the NOAEL observed in the rat single dose toxicity study and is 50-fold lower than the NOAEL observed in the rat and dog repeat dose toxicity studies.

Human dosimetry has been obtained in nine subjects. The results estimated an Effective Dose of 8.70 mSv for an anticipated 370 MBq (10 mCi) injection and is comparable to the effective dose of approved ¹⁸F-labeled compounds such as FDG and Florbetapir F 18 Injection.

The proposed dose has been shown to have acceptable image quality in previous human studies.

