5.3.2. Exclusion Criteria

Subjects will be excluded from enrollment if they:

- 1. Are aggressively being treated with life sustaining measures (e.g., receiving chemotherapy, currently on respirator; palliative chemotherapy is allowed);
- 2. Are known to have a structural brain lesion that would interfere either with PET imaging or pathological assessment. (Such lesions are typically > 2 cm at their greatest extent and may include stroke, primary or metastatic neoplasm, other tumors or cystic lesions. Subjects with a history of major stroke or other structural lesion as well as cases with a history of primary CNS neoplasm or known metastatic cancer must be discussed with the study sponsor prior to enrollment);
- 3. Have a clinically significant infectious disease, such as Human Immunodeficiency Virus (HIV) infection, hepatitis or prion disease;
- 4. Are currently receiving any investigational medications except with permission from the study sponsor;
- 5. Have ever participated in an experimental study with an amyloid or tau targeting agent (e.g., immunotherapy, secretase inhibitor);
- 6. Have suspected encephalopathy due to alcoholism or end-stage liver disease;
- 7. Are females of childbearing potential who are pregnant or not using adequate contraception;
- 8. Subjects who have a history of risk factors for Torsades de Pointes (TdP) (e.g., hypokalemia, family history of Long QT syndrome) or are taking drugs that are known to cause QT-prolongation (a list of prohibited and discouraged medications is provided by the Sponsor).

5.4. **Prior and Concomitant Therapy**

Except as noted in the exclusion criteria, all medications (prescription or over-thecounter) that have been started prior to screening may be continued during the course of the trial. All medications that are continued from the start of the trial or that are started during the trial (other than the study medication) must be documented in the case record form on the Concomitant Medication Page of the electronic Case Report Form (eCRF).

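### The Torsades/QT exclusion is written for enrollment only, and Protocol 7.1.4 does not say that newly meeting it bars the second injection

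*Protocol*

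**What the plan says.** **The precaution.** Protocol Section 1 reports a positive in vitro hERG assay and clean dog cardiovascular studies. It concludes that "until sufficient human cardiovascular safety data are available, clinical studies will exclude subjects with a history of risk factors for Torsades de Pointes", and likewise those taking drugs known to prolong the QT interval.

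**The criterion.** Section 5.3.2 opens its list with "Subjects will be excluded from enrollment if they". Item 8 covers a history of Torsades risk factors, with hypokalemia and a family history of long QT syndrome as examples. It also covers subjects "taking drugs that are known to cause QT-prolongation (a list of prohibited and discouraged medications is provided by the Sponsor").

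**Drugs during the trial.** Section 5.4 applies the exclusion criteria to medicines begun before screening. Medicines continued or "started during the trial (other than the study medication) must be documented in the case record form"; no other rule is given for them.

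**The second dose.** Section 5.1 allows a second scan at the sponsor's discretion and adds that "screening assessments will not need to be repeated". Section 7.1.4 repeats this, recommends a window of six to nine months after the first scan, and sets out what is done instead: "screening assessments will not be repeated. The procedures in Section 7.1.2 will be performed and updated medical history /concurrent medications", together with an updated neurological diagnosis, are collected. The imaging-visit procedures of 7.1.2 apply in full, including the 370 MBq target dose.

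**The concern.** The reason given for exclusion 8 is exposure to the drug, and the second injection is another exposure at the same target dose. Nothing in the protocol explains why the precaution would cover the first dose and not the second. On the visible rules, a subject who started a QT-prolonging drug or developed a Torsades risk factor after the first scan has that fact recorded, and the decision to inject is then left to individual judgment. What is at stake is subject safety and consistent handling across sites. Sample size, error rates and the primary analyses are not materially touched.

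**Working it through.** This is a question of wording, so the check sets the relevant provisions side by side.

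| Provision | Applies to second dose? | Names QT, Torsades or exclusion 8? | States a do-not-inject rule for it? |
|---|---|---|---|
| Protocol 1, rationale | Not addressed | Yes | No; speaks of excluding subjects |
| Protocol 5.3.2, item 8 | Written for enrollment | Yes | Only at enrollment |
| Protocol 5.4, drugs started during the trial | Yes | No | No; documentation only |
| Protocol 5.5, best-interest removal | Yes | No | No |
| Protocol 7.1.2, pre-dose physician assessment of tolerability | Yes | No | No |
| Protocol 7.1.4, sponsor discretion and updated history and drugs | Yes | No | No |
| Protocol 7.2, physician review of safety data | Yes | No | No |
| Protocol 7.7.2, dose request to the sponsor; adverse events collected up to the second dose | Yes | No | No |
| SAP 3.1 and 6.3, second-scan description | Yes | No | No |

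No row both covers the second dose and states the bar.

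**Contrast with pregnancy.** Section 7.1.2 makes a negative test a condition of each injection in females of childbearing potential, and Section 6 forbids giving the product to pregnant or lactating females. The protocol therefore does write per-injection bars. Exclusion 8 has none.

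**Other backstops.** The trial flow chart lists no ECG or laboratory panel, and SAP 16.2 and 16.3 mark both as not applicable. Vital signs are pulse, respiration and blood pressure. In the visible text, detection of a new QT risk at the second dose rests mainly on the history and medication update. SAP 3.1 places that update at the second imaging visit, so the sponsor's agreement and the dose request may come before it. The protocol does not say that the update precedes the injection.

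**Elapsed time.** Inputs: recommended interval of 6 to 9 months (7.1.4); 30.4375 days per month (SAP 11.1); follow-up call no earlier than 48 hours, or 2 days, after injection (7.1.2).

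- Interval between injections: 6 × 30.4375 = 182.6, about 183 days; 9 × 30.4375 = 273.9, about 274 days.
- Section 7.2 stops collection of history and medications after the follow-up call until death or consent to a second scan. If that consent is given at the second visit (an assumption), the longest period without collection is 182.6 − 2 = 180.6, about 181 days, to 273.9 − 2 = 271.9, about 272 days. Earlier consent shortens it.

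These are elapsed times, not measures of risk. The documents give neither the number of second injections nor the number of subjects who newly met exclusion 8.

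**The case against.** The strongest reply is that this is a drafting preference. Section 1 states a study-level precaution, and waiving repeat screening procedures such as the physical examination, MMSE and IQCODE does not say that safety exclusions lapse. The needed data are collected for the second scan. A physician sees the subject before dosing, and the sponsor, which issues the medication list, controls access to the second scan. Nothing obliges anyone to dose a known user of a QT-prolonging drug. Other exclusions also lack an express re-check, and a pregnancy test naturally carries a result condition. The days without collection matter little, because the update can capture what changed in between.

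The reply also rests on unseen documents. The sponsor's list may apply throughout the trial. SAP Section 9 has a deviation type for concomitant medication criteria, which suggests a rule may exist somewhere. The SAP is based on protocol amendment 3, whereas the protocol available is amendment 2. The investigator's brochure is not available either.

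Much of this stands, and it limits the point to a minor one. It does not supply the missing rule. Data collection without a stated consequence leaves the outcome to judgment, and the general checks do not direct that judgment to QT risk. Exclusion 8 is singled out because Section 1 ties it to a property of the drug itself.

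**Conclusion.** The point holds as a minor safety-wording gap. Exclusion 8 is framed as an enrollment criterion, and no text in the available documents says that newly meeting it bars the second injection. It should not be read as saying that no safeguard exists. The likely harm is low: Section 5.2.2 limits the mass dose to 20 µg, and Section 1 reports no QT prolongation in dogs at up to 50 times the maximum human dose. The number of subjects affected cannot be estimated, and there is no material effect on the primary analysis. Confidence is medium, because the conclusion assumes that neither the sponsor's medication list nor amendment 3 already carries the rule to the second dose.

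**What to change.** Add to Protocol 7.1.4: before the second injection, exclusion 8 is re-confirmed from the updated medical history and concurrent medications, and a subject who now meets it is not injected. Add one eCRF confirmation. If the sponsor's list already contains such a rule, the sentence can cite it.

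The cost is one sentence and one form item, using data already collected. The downside is that a few cognitively impaired subjects may lose the second scan and so leave the primary cohort if they die more than nine months after the first.

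SAP 7.1 reports that the stopping criteria had been met after the May 2018 consensus meeting. If second dosing is therefore finished, the sponsor can instead check the updated history and medication records of subjects injected twice, and correct the wording for later protocols.

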7.2. Observations and Measurements

Informed Consent

Potential subjects and LARs, if applicable, will be allowed to read a written informed consent form. The principal investigator or designee will explain all study procedures, risks, and alternative therapies to the subject and LAR, if applicable. The subject and LAR will have an opportunity to have all questions answered. The appropriate parties will then sign and date the informed consent form, indicating willingness to participate in the study and brain donation (see Section 7.5). A copy of the signed informed consent will be given to the subject and/or LAR.

All informed consent forms must be approved by Avid or designee, and by the appropriate Institutional Review Board (IRB) prior to use.

IQCODE - Short Version

Informant Questionnaire on Cognitive Decline in the Elderly (IQCODE; Jorm 1994) is a tool used to assess cognitive impairment in older people. IQCODE will be administered to the subject's caregiver/informant.

Mini-Mental State Examination (MMSE)

The MMSE (Folstein et al., 1975) is a brief instrument used to assess cognitive function in elderly patients. The instrument is divided into 2 sections. The first section measures orientation, memory, and attention. The maximum score for the first section is 21. The second section tests the ability of the patient to name objects, follow verbal and written commands, write a sentence, and copy figures. The maximum score for the second section is 9. The range for the total MMSE score is 0 to 30. The MMSE will be administered at screening to subjects that are able to cooperate with testing.

Medical History, Neurologic Disease History

The investigator or designee will obtain a case history at the screening visit. Whenever possible, the medical history will be confirmed by medical records.

- Relevant demographic information (e.g. birth year, gender, race, ethnicity, education);
- Social history/baseline characteristics (e.g. history of alcohol, drug use, and smoking, prior CSF or genetic testing results);
- Medical and surgical history;
- Concurrent medications;
- Neurologic Disease history (if relevant: date or months since symptom onset, date or months since diagnosis, family history of neurologic disease);

After the 48 hour follow-up phone call has been completed, additional medical history and concurrent medications will not be collected until death or unless the subject consents to a second ¹⁸F-AV-1451 PET scan.

Documentation of the events leading up to death will be collected.

Physical Examination

A brief physical examination will be conducted by a medically qualified study team member at the screening visit. Clinically significant changes from screening will be recorded as adverse events for the relevant study period.

Neurological Examination

A brief neurological examination will be performed by a medically qualified study team member at the screening visit to evaluate cranial nerves, gait, sensory, and motor function, coordination and tendon reflexes.

MRI

Historical brain MRIs that have been obtained within 12 months of the ¹⁸F-AV-1451 PET imaging visit and are available electronically will be sent to the designated imaging core lab if the subject provides consent.

Vital Signs

Vital signs (pulse rate, respiratory rate, blood pressure) will be taken in the supine position at the following time points:

- Screening Visit
- ¹⁸F-AV-1451 Imaging Visit
 - Immediately prior to the administration of ¹⁸F-AV-1451 Injection;
 - After the completion of imaging prior to discharge.

Height and Weight

At the screening visit the most recent body weight and height will be collected from the subject's medical record.

Optional Brain Tissue Research/Genetic Testing

Additional research and genetic testing is optional, and may be performed on brain tissue and will be outlined in the Neuropathology Analysis Plan or other vendor manual. Where local regulations allow, samples will be stored and analysis may be performed on genetic variants thought to play a role in dementia or related diseases. Samples will only be used for investigations related to disease and drug or class of drugs under study in the context of this clinical program. They will not be used for broad exploratory unspecified disease or population genetic analysis.

Samples will be identified by the subject number and stored for up to 15 years after the last subject visit for the study at a facility selected by the sponsor. The sample and any data generated from it can only be linked back to the subject by investigator-site personnel. The results of this testing will not be shared with the principal investigator or subjects' families.

Pregnancy Testing

A urine beta-hCG test will be performed at screening and at the ¹⁸F-AV-1451 imaging visit(s) prior to injection for females of childbearing potential (defined as premenopausal, less than 2 years post-menopausal or not surgically sterile). A serum pregnancy test may also be obtained prior to injection at the ¹⁸F-AV-1451 imaging visit(s) if required by the local site.

Physician Visit

At screening, a physician or designee must see the subject to evaluate their current medical status.

A physician must see the subject prior to drug administration and prior to discharge from the ¹⁸F-AV-1451 imaging session. At this time, the physician should review all safety data and briefly examine/query the subject regarding potential adverse events or other treatment issues.

Brain Autopsy

For those subjects who come to autopsy, brain harvesting will be performed locally by the site in accordance with the Technical Autopsy Manual and tissue will be sent to a pathology core lab(s) for neuropathological examination according to the Neuropathology Analysis Plan, which will be written prior to the first subject neuropathology analysis in this study. Autopsies will not be performed on subjects that live longer than nine months after the ¹⁸F-AV-1451 PET scan.

Brain tissue will be under custody of Avid Radiopharmaceuticals for up to 15 years for research purposes. During this time Avid may choose to transfer the brain tissue to another laboratory for additional study related research, or to a long term storage facility, or back to the clinical site or brain bank at which the subject was previously enrolled. Autopsy reports will be sent to the principal investigators to share with the subjects' families after the study has been completed.

